#### **Description of Population to be Enrolled:**

This study aims to enroll 24 subjects, 12 patients for each of the two treatment arms, all with documented stable juvenile osteochondritis dissecans identified via imaging. We believe 24 patients could be included during the time period allotted for the study based on the number of patients suffering from OCD seen annually at the Children's Hospital Sports Medicine Clinic.

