#### **Patient Recruitment**

A diagnostic knee MRI (through CHCO or an outside facility) will have been performed as standard of care prior to study participation, utilizing dGEMRIC, a Non-contrast MRI or a MRI with and without contrast in patients with a high clinical suspicion for osteochondritis dissecans. The study is posted on the clinicaltrials.gov website and patients and/or their parents may call and inquire about eligibility.

Lesions will be classified according to Di Paola et al classification [33]

This uses 5 stages as follows:

Grade 1: Small change of signal without clear margins of fragment,

Grade 2: osteochondral fragment with clear margins but without fluid between fragment and underlying bone,

Grade 3: fluid is visible partially between fragment and underlying bone,

Grade 4: fluid is completely surrounding the fragment, but the fragment is still in situ;

Grade 5: fragment is completely detached and displaced.

Only patients with Di Paola stage 1 or 2 lesions will be approached for study participation and consented into the study.

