### **Randomization**

After consent, the study personnel will open a sealed envelope containing the randomization assignment. The envelopes will also contain the appropriate patient handouts and instructions. Randomization will be balanced within the study to allow equal assignment to each treatment group. The randomization envelopes will be prepared by [name], the study biostatistician or her designated staff, using a random balanced allocation randomization protocol.

A study ID participant list in REDCap will be filled out by [name]/[name], their research staff or the Radiology Research Associate, [name], and will record the treatment assignment. The study personnel will e-mail the study statistician with the patient's study id number and the treatment assignment, recorded as 1 or 2. The study personnel will keep a key file containing the patients' names and study id numbers.

The study will not be blinded to the patient, to the patient's parent, or the physician administering the PRP injections. However, the study imaging and results will be kept blinded to the PI, [name], Pediatric Radiologist and the study biostatistician until the blind is broken, shortly before manuscript submission. Thus, treatment assignment will simply be recorded as 1 or 2 for the datasets.

The informed consent will make it clear to the patient and the patient's parents that the child will be randomized to one of two treatments: platelet-rich plasma injection with standard of care, or standard of care alone. Some patients may not like their assignment. If the patient wishes to, the patient who does not like their assignment can at that point drop out of the study and proceed with whatever care they choose. Such randomization related dropouts will be recorded.

This participant list in REDCap will contain the following information: At a minimum, empty columns are provided to record the following:

- Subject name
- Medical record number
- Patient and parent email addresses
- Initials of person enrolling the subject
- Date of enrollment.
- Treatment assignment
- List of required surveys to indicate completion

Other empty columns can be added on request.

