#### **Subject Study ID Assignment Log Sample:**

Assignment log will go from study ID 1 to study ID 24. Each one will correspond to a randomized number. Table 1 below is an example of the excel sheet that will be used.

Table 1 – Subject Study ID Assignment Log Sample						
Randomization #	Subject Name	MR#	Study ID	Treatment Assignment	Date Randomized	Initials
CH1			1	PRP		
CH2			2	PRP	i.	
CH3			3	PRP	ii.	
CH22			22	Conservative	iii.	
CH 23			23	Conservative		
CH 24			24	Conservative		

Once randomization is performed, a randomized assignment list will also be filled out. Each randomization number will correspond to either of two treatments (PRP-Conservative).

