### **6 month Research MRIs**

- If the patient received their initial diagnostic MRI by a Non-contrast MRI, the patient will receive a Non-contrast MRI at their 6 month research MRI visit.
- If the patient received their initial diagnostic MRI by a dGEMRIC MRI, the patient will receive a dGEMRIC MRI at their 6 month research MRI visit.
- If the patient received their initial diagnostic MRI by a MRI with and without contrast, the patient will receive a Non-contrast MRI at their 6 month research MRI visit.

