Each patient will have four values of GAG (T1GD) measured at the baseline MRI and again at the 6 month MRI, via dGEMRIC. The locations of the measurements will be designated using the lateral view of the femoral condyle as a clock face with the medial femoral condyle superior location being designated as 12 o'clock, the inferior location being designated as 6 o'clock and the anterior location being designated as 3 o'clock; the lateral view of the femoral condyle as a clock face with the lateral femoral condyle superior location being designated as 12 o'clock, the inferior location being designated as 6 o'clock and the anterior location being designated as 9 o'clock. The values will be measured at four locations: the medial side at a weight bearing surface, the medial side at a non-weight bearing surface of the posterior condyle (4 o'clock), the lateral side at a weight bearing surface, and the lateral side at a non-weight bearing surface of the posterior condyle (8 o'clock). The side with the lesion will be designated as the affected side, and the side without the lesion will be designated as the non-affected side. GAG (T1GD) will be measured on the affected weight bearing surface at the site of the lesion. GAG (T1GD) will be measured on the non-affected side at the corresponding weight bearing surface of the femoral condyle.

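### Balance between the arms is not guaranteed among dGEMRIC patients, the only ones who supply T1GD, the sole outcome modelled and powered for Aim 1

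*Combined protocol and SAP*

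**What the plan says.** **Allocation.** The target is stated under Description of Population: "This study aims to enroll 24 subjects, 12 patients for each of the two treatment arms". Under Randomization, "Randomization will be balanced within the study to allow equal assignment to each treatment group", with envelopes prepared "using a random balanced allocation randomization protocol". No block size and no stratification factor is given. The sample log is a single sequence: "Assignment log will go from study ID 1 to study ID 24".

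**Imaging.** Under Patient Recruitment, the diagnostic scan precedes study participation, may come from the Children's Hospital or from outside, and is done "utilizing dGEMRIC, a Non-contrast MRI or a MRI with and without contrast". The list under 6 month Research MRIs then ties the follow-up scan to the first one: "If the patient received their initial diagnostic MRI by a Non-contrast MRI, the patient will receive a Non-contrast MRI". A first scan with and without contrast also leads to a non-contrast follow-up. Only a dGEMRIC baseline leads to a 6-month dGEMRIC.

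**Outcome.** The section on the dGEMRIC research MRI says "Each patient will have four values of GAG (T1GD) measured at the baseline MRI and again at the 6 month MRI, via dGEMRIC", which the follow-up rule makes impossible for patients without a dGEMRIC baseline. The Aim 1 endpoint also allows change on the Di Paola classification, but the Aim 1 analysis section specifies a model for T1GD only. The Power Analysis names Aim 1 as the primary endpoint and uses T1GD only.

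**The concern.** The factor that decides whether a patient enters the Aim 1 model is known for everyone before an envelope is opened, yet the allocation does not use it. The 12:12 balance that the protocol secures is for all 24 patients. In the subset that the model can analyse, the split is left to chance.

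What is at stake is precision. For a fixed number of dGEMRIC patients, an uneven split gives a less precise treatment difference than an even one, and the loss hurts most when the subset is small. If very few patients have dGEMRIC, one arm could hold almost none of the T1GD data.

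**Working it through.** **Inputs from the documents:** 24 patients, 12 per arm; difference 85 ms; SD 50 ms; correlation 0.2 between the two scans; stated power 0.93 at a Type I error of 0.05 (Power Analysis); Aim 1 tests at 0.05/3 = 0.017 (Aim 1 analysis). Sidedness is not stated; two-sided is assumed. **Not in the documents:** the number K of dGEMRIC patients, here taken as 6, 8, 12, 16 or 20 of 24. Dropout is ignored.

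**1. The plan's own figure.** Power is from the noncentral t distribution with n1 + n2 − 2 degrees of freedom and noncentrality 85 / (50·√(1/n1 + 1/n2)). For 12:12 this is 85 / (50·√(1/6)) = 4.16.
- 6-month value, alpha 0.05: 0.978.
- 6-month value, alpha 0.05/3: 0.932.
- Change score, SD 50·√(2·(1 − 0.2)) = 63.2, alpha 0.05: 0.882.

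The stated 0.93 is thus not matched at the printed 0.05 two-sided, but is matched by the 6-month comparison at Aim 1's Bonferroni level. I use the 6-month comparison at 0.05 below and give the alternatives after the table.

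**2. Chance of an uneven split.** With 12 places per arm and MRI type unrelated to position on the list, the number x of dGEMRIC patients in the PRP arm is hypergeometric: P(x) = C(12,x)·C(12,K−x) / C(24,K).

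Example, K = 8, with C(24,8) = 735,471:
- 4:4 has probability 495² / 735,471 = 0.333.
- 5:3 either way has probability 2·792·220 / 735,471 = 0.474.
- A gap of 4 or more has the remainder, 1 − 0.333 − 0.474 = 0.193.

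**3. Cost of one poor draw.**
- K = 8: 4:4 has noncentrality 85 / (50·√(1/4 + 1/4)) = 2.40 and power 0.523. A 6:2 split has 85 / (50·√(1/6 + 1/2)) = 2.08 and power 0.417.
- K = 12: 6:6 gives 0.756, 8:4 gives 0.707 and 9:3 gives 0.634.

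**4. Average cost.** Weighting the power of each split by P(x):

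| dGEMRIC patients K | P(gap of 4 or more) | Power, even split | Average power, no stratification |
|---|---|---|---|
| 6 | 15.5% | 0.358 | 0.319 |
| 8 | 19.3% | 0.523 | 0.486 |
| 12 | 22.0% | 0.756 | 0.736 |
| 16 | 19.3% | 0.885 | 0.878 |
| 20 | 9.3% | 0.949 | 0.947 |

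At alpha 0.05/3 the pairs (even, unstratified) are 0.165 and 0.144; 0.296 and 0.269; 0.551 and 0.529; 0.743 and 0.732; 0.864 and 0.861. For the change score at 0.05 they are 0.246 and 0.220; 0.360 and 0.334; 0.557 and 0.538; 0.706 and 0.696; 0.811 and 0.808. In every variant the average loss is between 0 and 4 points.

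**5. A nearly empty arm.** For K = 6, with C(24,6) = 134,596, the chance that one arm has at most one T1GD patient is (2·924 + 2·12·792) / 134,596 = 20,856 / 134,596 = 15.5%. For K = 8 it is 2.7%, and for K = 12 about 0%.

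**6. Comparison with the loss of patients itself.** Going from 12:12 to 6:6 lowers power from 0.978 to 0.756, about 22 points. With those 12 patients, leaving the split to chance costs a further 2 points on average.

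**The case against.** The strongest reply is that this is a small matter. MRI type is fixed before randomisation, so the dGEMRIC subset is itself randomised and is balanced in expectation. The average power loss is 0 to 4 points and under 1 point once 16 or more patients have dGEMRIC. Stratification would not rescue Aim 1: a perfectly even split still gives only 0.36 with 6 patients and 0.52 with 8. The real damage is that non-dGEMRIC patients drop out of the T1GD model. The absence of strata is also read partly from silence and from a log labelled as a sample. All of this stands, and it sets the size of the point. It does not remove the point: the trial runs once, the chance of a gap of 4 or more is about one in five to one in six for K from 6 to 16, and the safeguard is nearly free.

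Four stronger readings are tempting, and the documents do not support them:
- **That the arms are unbalanced.** Nothing shows this; balance is only not guaranteed.
- **That the T1GD comparison is biased by referral.** Everyone in it had dGEMRIC, so an uneven split of MRI type changes only the group sizes. The documents do not tie scan type to the place of diagnosis. Confounding by MRI type could arise only in whole-trial comparisons such as Aim 2, and there only by chance.
- **That one arm may well have almost no T1GD data.** This is material only at about 6 dGEMRIC patients.
- **That T1GD is the only Aim 1 measure.** Di Paola change is also allowed; it has no Aim 1 model and no power calculation.

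**Conclusion.** The point holds as a cheap improvement, not as a flaw that invalidates Aim 1. The protocol describes balance only over all 24 patients, and does not guarantee it among those who supply the outcome that Aim 1 models and powers. The consequence is a modest average loss of power (0 to 4 points) and a 9% to 22% chance of a gap of at least 4 patients, with no systematic bias.

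These figures rest on an assumed dGEMRIC share, an overall list of exactly 12 and 12, MRI type arriving in an order unrelated to the list, the plan's own 85 ms and SD 50, and no dropout. The share matters most: with few dGEMRIC patients a poor draw is costly, and with most patients on dGEMRIC the effect is negligible. The larger problem, that the power analysis treats all 24 patients as having T1GD, is separate and remains whether or not the list is stratified.

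**What to change.** - Prepare two envelope series, one for patients with a dGEMRIC baseline and one for all others, each in small permuted blocks of varying size (for example 2 and 4). Open the next envelope in the patient's series. If enrolment has begun, apply this to the remaining envelopes.
- Include the MRI-type stratum as a factor in the Aim 2 models, where both strata are analysed together. The T1GD model needs no such factor.
- State the strata in the Randomization section. Keep the block sizes from the staff who open the envelopes.

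**Cost.** A second set of envelopes, a sentence or two of text and one more model term. A series stopped inside a block of 4 is out of balance by at most 2, so the overall split can end at 13:11 and, rarely, 14:10. With an even number of patients in each series, the overall split stays exactly 12:12 about 79% of the time. With odd numbers, each series ends one patient out in a random direction, so the two cancel half the time and otherwise give 13:11. Small blocks are also somewhat more predictable in a trial where the patient, the parent and the injecting physician know the treatment; varying the block size limits this.

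Separately, power should be restated for the number of dGEMRIC patients that the sponsor expects, because stratification cannot recover what is lost there.

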## **Participant Discontinuation Criteria**

Patients may be withdrawn from the trial for one of the following reasons:

1. Noncompliance with the protocol procedures
2. The patient has been given other or additional treatment, which may interfere with the study treatment (such as intra-articular steroid injection).
3. The patient wishes to withdraw from the trial
4. A severe adverse reaction by treatment applied is evident. Such as joint infection which requires IV antibiotics and possible surgical irrigation and drainage.
5. Patient becomes pregnant prior to completion of the third injection
6. Patients receiving conservative treatment whose lesion becomes unstable, requiring surgery during the study period will be excluded from participating in the remainder of the study
7. The investigator may withdraw patients from the trial if it is in the best interest of the patients. The reason for withdrawal shall be clearly described and the patient shall, whenever possible irrespective of the reason for withdrawal, as soon as possible be called for a final visit. All relevant assessments shall be completed, preferably according to the schedule for the final visit.

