### **b. Risks Associated with dGEMRIC MRI and Non-contrast MRIs**

The initial MRI performed for this study is considered standard of care in the management of knee osteochondritis dissecans. The follow-up MRI at 6 months is for research purposes.

If a patient receives a dGEMRIC MRI, the gadolinium based contrast agents used for this type of imaging can result in nausea, vomiting, cutaneous rashes, shortness of breath, or chest pain, all of which are considered very rare [35]. Death attributed to gadolinium based contrast agents is extremely rare, “The overall rate of gadolinium-based contrast agent deaths reported to the FDA Medwatch database is less than 1 in a million (40 deaths in 51 million administrations), similar to the risk of death from a chest radiograph, drinking one half liter of wine, smoking 1.4 cigarettes ([tobaccodocuments.org/lor/03732381-2387.html](http://tobaccodocuments.org/lor/03732381-2387.html)), or traveling 86 miles by car ([www-nrd.nhtsa.dot.gov/Pubs/811291.PDF](http://www-nrd.nhtsa.dot.gov/Pubs/811291.PDF)).”

The specific gadolinium based contrast agent used at Children’s Hospital Colorado, gadobenate dimeglumine (MultiHance), was recently evaluated for safety in children without any adverse effects observed during the first twenty-four hours after contrast administration [36].

Nephrogenic systemic fibrosis is a fibrosing disorder associated with exposure to gadolinium-based contrast agents in people with severely compromised renal function [36]. There have been seventeen documented cases in patients 18 years or younger with documented exposure to gadolinium-based contrast agents [37]. Proposed risk factors are dialysis patients with GFR below 30 mL/min, high-dose gadolinium, proinflammatory conditions, acute renal failure, postoperative state, and hyperphosphataemia. The American College of Radiology recommends that people with severe chronic kidney disease (eGFR <30 mL/min/1.73 m^2) or acute kidney injury should avoid exposure to gadolinium-based contrast agents. The American College of Radiology recommends that people with severe chronic kidney disease (eGFR <30 mL/min/1.73 m^2) or acute kidney injury should avoid exposure to gadolinium-based contrast agents [37].

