### **Power Analysis**

We conducted a power analysis for Aim 1, the primary endpoint of the study. The maximum sample size for the proposed trial is fixed at 12 patients per arm (24 participants total). The sample size is limited due to costs associated with dGEMRIC.

We calculated power for the test of no difference in T1GD between the treatment groups. We assumed a standard deviation of 50 ms for T1GD values, and a correlation of 0.2 between the baseline MRI and the 12-month T1GD measurements. Estimates were based on T1GD values reported by Neuman et al[42]. We expect T1GD values to be 85 ms higher in the injection group when compared to conservative therapy at the 6 month time point with no difference at baseline. We calculated power for 10, 11, or 12 participants per arm. Power was calculated using GLIMMPSE version 2.0.1.[43]

To detect a mean difference of 85 ms in T1GD between the treatment groups, power will be 0.93 with a Type I error rate of 0.05, for 12 participants per treatment group. To ensure a conclusive study, we will target an effective sample size of 10 participants per group. Over the 12 months, we expect to lose up to two participants per treatment group. To account for the attrition, we have set an enrollment goal of 24 participants, or 12 participants per treatment group.

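### Patients may leave after learning their open assignment, and the plan states no 6-month follow-up, analysis as randomised or sensitivity analysis for them, so the comparison of those who remain may be biased

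*Combined protocol and SAP*

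**What the plan says.** The section *Randomization* fixes the order of events: "After consent, the study personnel will open a sealed envelope containing the randomization assignment". It also says "The study will not be blinded to the patient", and the same holds for the parent and the injecting physician. It foresees that some families will be disappointed and provides that "the patient who does not like their assignment can at that point drop out of the study and proceed with whatever care they choose". The stated follow-through is that "Such randomization related dropouts will be recorded".

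*Participant Discontinuation Criteria* includes the patient's own wish to withdraw among its reasons. It adds that "the patient shall, whenever possible irrespective of the reason for withdrawal, as soon as possible be called for a final visit" and that "All relevant assessments shall be completed, preferably according to the schedule for the final visit".

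On the outcome scan, the section on MRI risks says "The follow-up MRI at 6 months is for research purposes". *Research Methods* likewise lists it among the three procedures that are not routine care.

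*Power Analysis* says "Over the 12 months, we expect to lose up to two participants per treatment group". It does not separate refusals of the assignment from later loss. The *Data Analysis Plan* and the sections for Aims 1 to 3 define no all-randomised analysis set, no rule to analyse patients in the assigned arm, and no missing-data or sensitivity analysis.

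**The concern.** Randomisation makes the two groups comparable at the moment the envelope is opened. This plan allows an exit just after that moment, for a reason tied to the assignment. Only one arm offers the new treatment, so unequal refusal is plausible. Those who refuse may also differ in symptoms or motivation. The right to withdraw does not oblige the plan to lose their outcomes, because declining a treatment and declining follow-up are separate decisions.

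With 12 patients per arm, each refuser is 1/12 = 8.3% of the arm. The estimated effect could shift for reasons unrelated to PRP, and the plan gives the reader no means of judging by how much.

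**Working it through.** **1. What a refuser at envelope opening would contribute**

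- *Final visit.* It is to be held as soon as possible, so it falls near baseline. It supplies neither the 6-month MRI nor the scores from 6 weeks to 12 months.
- *Aim 2 model.* The visits listed are 6 weeks, 12 weeks, 6, 9 and 12 months. Baseline is not among them, so a patient with only near-baseline data adds nothing.
- *Aim 1 model.* The initial MRI is a modelled visit. A refuser whose diagnostic scan was dGEMRIC can contribute a baseline T1GD value, under missing-at-random. The assumed correlation with follow-up is 0.2, so this value says little about 6 months. A refuser with a non-contrast diagnostic scan has no T1GD value.

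**2. The plan's own figures** (*Power Analysis*: difference 85 ms, SD 50 ms, correlation 0.2, alpha 0.05, 12 per group, power 0.93)

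- Enrolment: 10 / (1 − 2/12) = 12 per group. This reproduces.
- Power, two-sample noncentral t, two-sided 0.05: 0.978 for the 6-month value alone, 0.982 for ANCOVA, and 0.882 for the change from baseline (SD 50 × √(2 × (1 − 0.2)) = 63.2 ms). None equals 0.93. The nearest variants are 0.939 (change, one-sided 0.05) and 0.933 (6-month value, two-sided 0.017). The plan does not state sidedness. The present point does not depend on which variant was used.

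**3. Bias if refusers are lost**

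Let f of 12 patients in one arm refuse, and let D be the refuser mean minus the completer mean at 6 months. The full-arm mean is the completer mean + (f/12) × D, so dropping refusers biases that arm by (f/12) × D in size. The documents give neither f nor D; both are assumed here. For the false-positive rate there is no true effect, the 6-month value is compared by t-test with 12 v 12 − f patients, SD 50 ms, two-sided 0.05, and noncentrality bias / (50 × √(1/12 + 1/(12 − f))).

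| Refusers f | Bias, D = 50 ms | False-positive rate | Bias, D = 85 ms | False-positive rate |
|---|---|---|---|---|
| 1 | 4.2 ms | 0.054 | 7.1 ms | 0.062 |
| 2 | 8.3 ms | 0.066 | 14.2 ms | 0.097 |
| 4 | 16.7 ms | 0.106 | 28.3 ms | 0.217 |

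The sign is open. If conservative-arm refusers would have done better than those who stay, PRP is flattered. If they would have done worse, the bias runs against PRP. The table also assumes that all 12 per arm would have T1GD values, as the power analysis does. With fewer dGEMRIC patients, each refuser among them weighs more.

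**4. Loss of power** (change from baseline, SD 63.2 ms, two-sided 0.05)

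12 v 12: 0.88. 12 v 10: 0.85. 10 v 10: 0.81. 12 v 8: 0.80. 10 v 6: 0.68. Two refusals in an arm leave 12 − 2 = 10, the effective target, before follow-up has begun.

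**5. Price of analysing everyone as assigned**

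Assume f of 12 conservative patients obtain the full PRP effect elsewhere. The difference becomes 85 × (1 − f/12): 77.9, 70.8 or 56.7 ms for f = 1, 2 or 4. Power for the same contrast, all 24 followed, is 0.82, 0.75 or 0.56.

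**The case against.** Several stronger readings are tempting, and the documents do not support them.

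- *That nothing is collected on these patients.* The discontinuation section asks for a final visit with assessments whatever the reason. The schedule text also calls the KOOS and IKDC surveys standard of care, although Table 3 labels them research. Later survey data are therefore not excluded; they are simply not planned for. The consent form is not among the pages available, so its silence cannot be counted against the plan.
- *That refusers drop out of every model.* This fits Aim 2, but a refuser with a baseline dGEMRIC scan can stay in the Aim 1 model.
- *That the arms are self-selected.* No refusal rate, imbalance or prognosis is given. The PRP arm brings three blood draws and three knee injections for patients aged 10 to 17, so refusal there is plausible too.
- *That two or three losses shift the control mean by 0.30 or 0.42 SD.* This is the truncated-normal result φ(z)/(1 − f), with f = 2/12 or 3/12 here the fraction removed, when exactly the most symptomatic patients leave. Order statistics for n = 12 (1.629, 1.116, 0.793) give (1.629 + 1.116)/10 = 0.27 and (1.629 + 1.116 + 0.793)/9 = 0.39. Both are upper bounds on the score used for selection, not on the 6-month outcome. If selection were on baseline T1GD, a correlation of 0.2 would reduce them to about 0.05 to 0.08 SD, or 3 to 4 ms. Losing the most symptomatic controls would also work against PRP.

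It is also fair that the plan allows for two losses per arm and records both dropouts and assignment, so refusals by arm could be reported. None of this supplies 6-month outcomes for refusers or says how they are to be analysed.

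**Conclusion.** The concern holds as a risk of bias. The plan permits exit in response to a known assignment, and its prompt final visit does not deliver the 6-month MRI or the later scores for someone who leaves at once. It states no analysis as randomised and no sensitivity analysis. The comparison of those who remain may be biased if refusal differs by arm and relates to prognosis; the documents do not show that either will happen.

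With one or two refusers differing by 1 SD, the bias is modest: 4 to 8 ms against 85 ms. With four, it is about 17 ms and the nominal 0.05 error rate roughly doubles. These sizes rest on assumed numbers of refusers and an assumed difference from completers. The exhausted attrition allowance after two refusals follows from the plan's own figures. This should be corrected, but it does not undermine the trial by itself.

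**What to change.** - State that declining or changing the assigned care is separate from leaving follow-up. Ask such patients, without requiring it, to continue the scheduled surveys and the 6-month MRI.
- Define an analysis set of all randomised patients, each analysed in the assigned arm.
- Complete the baseline surveys before the envelope is opened. Table 3 appears to place both at the same visit without an order. This allows refusers to be compared with those who stay.
- Report refusals by arm.
- Add a missing-data sensitivity analysis, for example one that shifts refusers' unobserved 6-month values over a stated range such as ±50 ms.

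The cost is protocol and consent wording; the MRIs and surveys for all 24 patients are already planned. The downside is that the estimate then includes patients who did not take the assigned care, which dilutes the difference as shown in step 5 of the working. Some patients will still decline all follow-up, which is why the sensitivity analysis is needed.
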